2.4.4 Change in imaging modality

Per RECIST 1.1, a change in methodology can be defined as either a change in contrast use (e.g. keeping the same technique, like CT, but switching from with to without contrast use or vice-versa, regardless of the justification for the change) or a change in technique (e.g. from CT to MRI, or vice-versa), or a change in any other imaging modality. A change in methodology will result by default in an UNK (unknown) calculated overall lesion response assessment. However, another response assessment than the Novartis calculated UNK response may be accepted from the investigator or the central blinded reviewer if a definitive response assessment can be justified based on the available information.

2.4.5 Determination of missing adequate assessments

The term ‘missing adequate tumor assessment’ is defined as a tumor assessment not done or tumor assessment with overall lesion response ‘Unknown’. For the sake of simplicity, a ‘missing adequate tumor assessment’ will also be referred to as a ‘missing assessment’.

As described in Table 14-9 in Appendix 3 of the study protocol, the PFS censoring and event date options depend on the presence and the number of missing tumor assessments (TAs). In the analysis of PFS, an event occurring after two or more missing assessments or non-adequate tumor assessments is censored at the last adequate tumor assessment.

An exact rule to determine whether there is no, one or two missing TAs is therefore needed. This rule is based on the time interval between the last adequate tumor assessment (LATA) date and the event date. The scheduled date of tumor assessments (in weeks from randomization), protocol specified windows for tumor assessments, and the thresholds for LATA to belong to a visit can be found in the following table.

Schedule for tumor assessment and time windows

Assessment schedule		Scheduled date – 1 week	Scheduled date (weeks from randomization)	Scheduled date +1 week	Threshold (weeks)*
Every 8 weeks for the first 18 months	Baseline	0	0^	1	n/a
	C3D1	7	8	9	12
	C5D1	15	16	17	20
	C7D1	23	24	25	28
	C9D1	31	32	33	36
	C11D1	39	40	41	44
	C13D1	47	48	49	52
	C15D1	55	56	57	60
	C17D1	63	64	65	68
	C19D1	71	72	73	78
	C22D1	83	84	85	90

Every 12 weeks after 18 months	C25D1	95	96	97	102
	C28D1	107	108	109	114
	C31D1	119	120	121	126

* The mid-point between current and next visit (except for baseline) and the upper limit for LATA to be matched to a certain scheduled assessment, e.g. if LATA is at week 13, this is after threshold for C3D1 and before that for C5D1, so the matching scheduled assessment is C5D1.

^ Day of randomization is taken as 0.

To calculate the number of missing tumor assessments, the LATA before an event is matched with a scheduled tumor assessment using the time window in the table above (essentially whichever scheduled assessment it is closest to).

Two additional thresholds, D1 and D2 are calculated for that scheduled assessment based on the protocol-specified schedule and windows.

- The threshold D1 is defined as the protocol-specified time interval between the TAs plus 2x the protocol-allowed time window around the assessments.
- The threshold D2 is defined as twice the protocol-specified time interval between the TAs plus 2x the protocol-allowed time window around the assessments (except when the matched scheduled tumor assessment is C17D1, in which case D2 is defined in Rule 2 below).

Since there is a change of schedule for tumor assessments after 18 months, D1 and D2 are defined differently depending on when LATA occurs.

Rule 1: if LATA happens within 60 weeks from randomization (the matched scheduled tumor assessment is C15D1 or before). For example, D1=8+2=10 weeks and D2=2*8+2=18 weeks.

Rule 2: if LATA happens after 60 weeks but within 68 weeks from randomization (the matched scheduled tumor assessment is C17D1). For example, D1=8+2=10 weeks and D2=8+12+2=22 weeks.

Rule 3: if LATA happens after 68 weeks from randomization (the matched scheduled tumor assessment is C19D1 or later). For example, D1=12+2=14 weeks and D2=2*12+2=26 weeks.

The number of missing events is defined as:

- An event after LATA+D1 weeks will be considered as having ≥ 1 missing assessment
- An event after LATA+D2 weeks will be considered as having ≥ 2 missing assessments

The same definition of D2 will be used to determine the PFS censoring reason. If there is no post-baseline adequate tumor assessment available (before an event or a censoring reason occurred), the randomization date will be used to compute the interval.

If the time interval between the last adequate TA date and the earliest of the following dates is smaller or equal to D2 days:

Analysis cut-off date

Date of consent withdrawal

Visit date of study treatment discontinuation due to lost to follow-up or end of post-treatment follow-up discontinuation due to lost to follow-up.

Then the PFS censoring reason will be respectively:

- ‘Ongoing’
- ‘Withdrew consent’
- ‘Lost to follow-up’

However if the time interval is larger than D2 days with no event then the PFS censoring reason will always default to ‘Adequate assessment no longer available’. If the time interval between the last adequate tumor assessment date and the PFS event date is larger than D2 then the patient will be censored and the censoring reason will be 'Event documented after two or more missing tumor assessments'.

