Imaging assessments as described in [Table 7-2](#) should be performed using the same imaging modality used at baseline, irrespective of study treatment interruption or actual dosing (see [Table 7-1](#)). Imaging assessments for response evaluation will be performed every 8 weeks (+/- 7 days) after randomization during the first 18 months and every 12 weeks (+/- 7 days) until 36 months, then change to as clinically indicated. The 8-week (or 12 week) interval should be respected regardless of whether study treatment is temporarily withheld or unscheduled assessments are performed.

Additional imaging assessments may be performed at any time during the study at the investigator's discretion to support the efficacy evaluations for a subject, as necessary. Clinical suspicion of disease progression at any time requires a physical examination and imaging assessments to be performed promptly rather than waiting for the next scheduled imaging assessment.

Each lesion that is measured at baseline must be measured by the same method (either same imaging method or by photography, including a metric ruler) and when possible, the same local radiologist/physician throughout the study so that the comparison is consistent. If an off-schedule imaging assessment is performed because progression is suspected, subsequent imaging assessments should be performed in accordance with the original imaging schedule.

Combined Positron Emission Tomography/Computed Tomography (PET/CT) may be used only if the CT is of similar diagnostic quality as a CT performed without PET, including the utilization of IV contrast media. At the discretion of the Investigators, FDG-PET scans may be performed to document progressive disease per RECIST 1.1 ([Appendix 3](#)).

All study imaging (including any off-schedule imaging studies) should be submitted to the designated imaging CRO for quality control promptly after acquisition. If an off-schedule imaging assessment is performed to confirm response or if progression is suspected, subsequent imaging assessments should be performed in accordance with the original imaging schedule.

Table 7-2 Imaging assessment collection plan

Procedure	Screening:*** Day-28 to Day -1	Treatment phase	End of treatment	Post-treatment follow-up phase: Efficacy

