Table 4-1 Operating characteristics for PFS futility criteria in the PIK3CA mutant cohort	96
Table 4-2 Operating characteristics for PoC criteria in PIK3CA non-mutant cohort.....	98
Table 4-3 Local versus central disease progression assessments	99

List of figures

Figure 1-1	Study design	16
------------	--------------------	----

List of abbreviations

AE	Adverse event
AESI	Adverse event of Special Interest
ATC	Anatomical Therapeutic Chemical
BIRC	Blinded Independent Review Committee
BOR	Best overall response
CI	Confidence Interval
CBR	Clinical benefit rate
CR	Complete response
CRF	Case Report Form
CRO	Contract Research Organization
CRS	Case retrieval strategy
CSR	Clinical study report
CT	Computed tomography
CTCAE	Common Terminology Criteria for Adverse Events
CV	Coefficient of variation
ΔQTcF	Change from baseline in QTcF
DAR	Dosage administration Record
DI	Dose Intensity
DMC	Data Monitoring Committee
ECG	Electrocardiogram
ECOG	Eastern Cooperative Oncology Group
EORTC QLQ-C30	European Organisation for Research and Treatment of Cancer's core quality of life questionnaire
EOT	End of treatment
FAS	Full analysis set
HER2	Human epidermal growth factor receptor 2
HR.	Hazard Ratio
HRQoL	Health-Related Quality of Life

IRT	Interactive Response Technology
LLOQ	Lower Limit of Quantification
MedDRA	Medical Dictionary for Regulatory Activities
MRI	Magnetic resonance imaging
NMQ	Novartis MedDRA queries
NSAI	Non-steroidal aromatase inhibitor
ORR	Overall response rate
OS	Overall survival
PAS	Pharmacokinetic analysis set
PD	Progressive disease
PDI	Planned dose intensity
PFS	Progression-free survival
PK	Pharmacokinetic
PPS	Per Protocol Set
PR	Partial response
PRO	Patient Reported Outcome
PS	Performance Status
PT	Preferred term
QTcF	QT interval corrected by Fridericia method
RDI	Relative dose intensity
RECIST	Response Evaluation Criteria In Solid Tumors
SAE	Serious adverse event
SAP	Statistical Analysis Plan
SD	Stable disease
SD	Standard deviation
SMQ	Standardized MedDRA queries
SOC	System organ class
TA	Tumor assessment
TEAE	Treatment-emergent adverse event
UNK	Unknown

1 Introduction

This document describes the detailed statistical methodology to be used for the Clinical Study Report (CSR) for the analysis of study CBYL719C2301.

The content of this SAP is based on protocol CBYL719C2301 Amendment 5. All decisions regarding analysis, as defined in the SAP document, have been made prior to database lock and unblinding of the study data.

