2.4.3 Best overall response (BOR)

The evaluation of BOR will be assessed using RECIST 1.1. The definitions and the details on the derivation of BOR are given in Appendix 3 of the study protocol.

The best overall response will usually be determined from response assessments undertaken while on treatment. In addition, only tumor assessments performed before the start of any further anti-neoplastic therapies (i.e. any additional secondary anti-neoplastic therapy with the exception of palliative radiotherapy) will be considered in the assessment of BOR.

Further anti-neoplastic therapies will be identified from the data collected on ‘Antineoplastic therapy since discontinuation of study treatment- Medication’ eCRF and “Antineoplastic Therapy - Radiotherapy” eCRF.

Palliative radiotherapy is the only setting of radiotherapy allowed during a study. It will not be considered as an antineoplastic therapy for the assessment of BOR.

Continuation of fulvestrant monotherapy as 1st new anti-neoplastic therapy after end of treatment without prior PD and collected in the ‘antineoplastic therapy since discontinuation of study treatment- Medication’ eCRF, will not be considered as an anti-neoplastic therapy for the assessment of BOR.

Since the tumor assessments are performed every 8 weeks (+/- 7 days) after randomization during the first 18 months and every 12 weeks (+/- 7 days) thereafter, the standard definition of a best overall response evaluation of “stable disease”, “progressive disease” or “unknown” given in the Appendix 3 of the study protocol requires an adjustment. Best overall response for each patient is determined from the sequence of overall (lesion) responses according to the following rules:

- CR = at least two determinations of CR at least 4 weeks apart before progression
- PR = at least two determinations of PR or better at least 4 weeks apart before progression (and not qualifying for a CR)
- SD = at least one SD assessment (or better) > 7 weeks after randomization date (and not qualifying for CR or PR).
- Non-CR/non-PD = at least one non-CR/non-PD assessment (or better) > 7 weeks after randomization date (and not qualifying for CR or PR). This applies only for patients with non-measurable disease alone at Baseline.
- PD = progression ≤ 17 weeks after randomization date (and not qualifying for CR, PR, SD or non-CR/non-PD).

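### SAP 2.4.5 was not updated to the protocol Amendment 5 scan schedule, so at late cut-offs some PFS events are censored as following two missed scans that were never scheduled

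*SAP*

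**What the plan says.** The SAP introduction states: "The content of this SAP is based on protocol CBYL719C2301 Amendment 5". Under that protocol (section 7.2.1.1, with the same schedule in sections 4.1.4, 7.1.6 and Table 7-2), imaging is 8-weekly for 18 months and then "every 12 weeks (+/- 7 days) until 36 months, then change to as clinically indicated".

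The SAP does not carry the month-36 stop:

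- Section 2.4.3 still has scans "every 12 weeks (+/- 7 days) thereafter". Sections 3.8.1.6.1 (missing-scan summary) and 3.8.2.9 (patient-reported outcomes) also run 12-weekly without end.
- The visit table in section 2.4.5 ends at C31D1, week 120.
- A missing assessment "is defined as a tumor assessment not done or tumor assessment with overall lesion response" of unknown, but the number missed is inferred from time since the last adequate tumor assessment (LATA). Rule 3 covers the case "if LATA happens after 68 weeks from randomization" and sets "D1=12+2=14 weeks and D2=2*12+2=26 weeks".
- The consequence is stated as: "An event after LATA+D2 weeks will be considered as having ≥ 2 missing assessments".

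Under the primary censoring option C2(1) in section 3.8.1.1, such an event is censored at LATA. An event-free patient whose gap from LATA exceeds D2 is given the censoring reason *Adequate assessment no longer available* instead of *Ongoing*.

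**The concern.** D1 and D2 are meant to express the protocol's scan interval plus its windows. After month 36 the protocol has no interval, yet the rule keeps using 12 weeks. Elapsed time then stops being a proxy for missed scans: a patient who follows the protocol exactly can pass 26 weeks without a scan, and a later progression or death is removed from the analysis. Protocol Appendix 3 (section 14.3.40) ties the related censoring reason to planned assessments that were not available, so the SAP rule also departs from the concept it implements.

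What is exposed is late PFS reporting: PFS at the final-OS cut-off, and the COVID-19 PFS sensitivity analysis in SAP 3.8.1.5, which SAP Amendment 5 introduced for that cut-off. A COVID-19 death more than 26 weeks after the last adequate scan would already be censored in the base analysis, so the sensitivity analysis could not show its effect. The summary of censoring reasons would also suggest poor scan compliance where there was none.

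**Working it through.** **1. The SAP's thresholds.** D1 is one interval plus twice the 1-week window; D2 is two intervals plus twice the window.

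- Rule 1: 8 + 2 = 10 and 2×8 + 2 = 18 weeks.
- Rule 2: 8 + 2 = 10 and 8 + 12 + 2 = 22 weeks.
- Rule 3: 12 + 2 = 14 and 2×12 + 2 = 26 weeks.

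All agree with the SAP.

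**2. The last scheduled scan.** With the SAP's month of 30.4375 days, month 36 is 36 × 30.4375 / 7 = week 156.5. Continuing the table 12-weekly from week 120 gives weeks 132, 144 and 156 (C40D1), and then none.

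**3. Rule 3 against scans actually scheduled (Amendment 5 schedule).**

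| LATA (week) | Censored if event after week | Scheduled scans missed by then | Rule 3 says |
|---|---|---|---|
| 132 | 158 | 2 (weeks 144, 156) | 2 or more: right |
| 144 | 170 | 1 (week 156) | 2 or more: wrong |
| 156 | 182 (month 41.9) | 0 | 2 or more: wrong |

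Misclassification starts with a LATA matched to week 144 and needs a gap of more than 26 weeks.

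**4. Primary PFS.** Final PFS is planned about 32 months after first randomization, when the longest follow-up is about 31.9 months. Nobody has reached month 36.

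**5. Events exposed at later cut-offs (mutant cohort).** Inputs: exponential PFS with medians 7.0 and 11.67 months; accrual of 5, 14 and 24 per month (SAP 3.14) to 340; 1:1 allocation. Worst case: every patient's last scan is at week 156, none follows, and the month-36 stop applies throughout.

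- Accrual is 6×5 + 6×14 = 114 by month 12, then 24 per month, ending at 12 + (340 − 114)/24 = month 21.4.
- At month 54, patients at least 36 months from randomization number 114 + 24×6 = 258. Event-free proportions at month 36 are 2^(−36/7) = 2.8% and 2^(−36/11.67) = 11.8%, so about 129 × 0.028 + 129 × 0.118 = 19 patients.
- Week 182 is 182 × 7 / 30.4375 = 41.86 months. Expected wrongly censored events per arm = Σ ½[S(41.86) − S(fᵢ)] over patients whose follow-up fᵢ exceeds 41.86 months. Ignoring loss to follow-up, month 54 gives 0.3 control and 1.1 alpelisib.
- Adding 10% loss over 32 months (rate −ln(0.9)/32 = 0.0033 per month) gives about 0.2 to 0.3 and 1.0 at month 54, and about 0.7 and 2.6 to 2.7 at month 60.

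**6. Effect on the hazard ratio.** In simulation under these inputs the mean hazard ratio moves from 0.6001 to 0.5998 at month 54 and from 0.6014 to 0.6006 at month 60. The standard error of the log hazard ratio is about 0.115. The average change stays below 0.001 whether event-free patients are carried to their last follow-up or censored at the week-156 scan.

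**7. Whether another analysis recovers the events.** The actual-event analysis in SAP 3.8.1.5, option C2(3), would count them, but it runs only if more than 10% of patients (34 of 340) have two or more consecutive missing assessments before an event. About 19 exposed patients cannot trigger it alone.

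**The case against.** **The effect is narrow, and no confirmatory decision depends on it.** This stands. Clinically indicated scans reset LATA, suspected progression requires prompt imaging, and Table 7-2 mandates an end-of-treatment scan if the last non-progressing scan is more than 21 days old. PFS testing is confined to the planned PFS looks, and the protocol's Amendment 5 rationale says that the primary endpoint had been met. The reported median and the 6-, 12- and 18-month rates are unlikely to notice the rule.

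**The calendar shrinks it further.** This also stands. The first patient was screened on 23 July 2015, so month 54 falls at about the start of 2020. Amendment 5 is dated 11 February 2020 and needed ethics approval before implementation. The counts in step 5 treat the stop as in force throughout and so overstate exposure at months 54 and 60; only later cut-offs could be fully exposed.

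**Rule 3 introduces its numbers as examples, so programmers could adapt it.** This does not rescue the text. The protocol offers no interval after month 36 to substitute, and 26 weeks is the only value given.

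A reader might infer that after month 36 no scan can be missing for anyone. The dates do not support that: 214 mutant-cohort patients had been randomized by 14 December 2016, so those still followed passed month 36 by 14 December 2019, before the amendment. On the schedule that the SAP retains, they were still due 12-weekly scans, which could truly be missed.

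**Conclusion.** The mismatch is real: the SAP names Amendment 5 as its basis but applies a missing-scan rule that does not fit the Amendment 5 schedule. At late cut-offs it can censor genuine events and mislabel censoring reasons. The consequence is small: about 1 event at month 54 and about 3 at month 60, mostly on alpelisib, with an average hazard-ratio change below 0.001. These sizes rest on the design medians, planned accrual, 10% loss, no scan after week 156, and a stop in force from the start.

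Two stronger readings are tempting. One is that all progressions after month 36 are censored. They are not: with a last scan at week 156, every event up to week 182 still counts. The other is that the rule biases PFS in favour of alpelisib because more alpelisib patients remain event-free. The average shift is nominally in that direction, but it is negligible against the sampling error, and in a single trial it could go either way. No material bias is claimed, and primary PFS is untouched.

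**What to change.** In SAP 2.4.5:

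- Extend the schedule table to week 156 (C40D1).
- Count as missing only scans that were scheduled for that patient under the protocol version in force at the time: 12-weekly beyond month 36 until Amendment 5 took effect at the site, none after that.
- Count an event with fewer than two such missed scans at its actual date.
- Derive the censoring reasons from the same count, so that an event-free patient on schedule is *Ongoing*.

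Align the schedule wording in SAP 2.4.3, 3.8.1.6.1 and 3.8.2.9 with the 36-month schedule.

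The cost is SAP wording, a modest programming change, and one extra input: the date on which Amendment 5 took effect at each site. No new patient data are needed, and the primary PFS analysis does not change.

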2.4.6 No baseline tumor assessments

As specified in Table 14-9 in Appendix 3 of the study protocol, since the timing of disease progression cannot be determined for patients with missing baseline tumor assessment, these patients are censored in the PFS analysis at the date of randomization. This rule, however, only applies to the ‘progressive disease’ component of the PFS assessment.

Patients without any baseline tumor assessment who die within D2 time interval ([Section 2.4.5](#)) from date of randomization will be counted as having an event in the analysis of PFS at the date of death. All deaths will be counted in the overall survival analysis regardless of presence or absence of the baseline tumor assessment.

2.4.7 Construction of waterfall graphs

Waterfall graphs will be used to depict the anti-tumor activity. These plots will display the best percentage change from baseline in the sum of diameters of all target lesions for each patient. Only patients with measurable disease at baseline will be included in the waterfall graphs.

Special consideration is needed for assessments where the target lesion response is CR, PR or SD, but the appearance of a new lesion or a worsening of non-target lesions results in an overall lesion response of PD. As a conservative approach, such assessments will not be considered for display as bars in the graph, since the percentage change in the sum of diameters of target lesions reflects the non-PD target lesion response, but the overall lesion response is PD. A patient with only such assessments will be represented by a special symbol (e.g. *) in the waterfall graph.

Assessments with “unknown” target lesion response and assessments with unknown overall response will be excluded from the waterfall plots. Patients without any valid assessments will be completely excluded from the graphs.

The total number of patients displayed in the graph will be shown and this number will be used as the denominator for calculating the percentages of patients with tumor shrinkage and tumor growth. Footnote will explain the reason for excluding some patients (due to absence of any valid assessment).

All possible assessment scenarios are described in [Table 2-2](#).

Table 2-2 Assessments considered for calculation of best percentage change for waterfall graphs

Case	Target response	Overall lesion response	Calculate % change from baseline in sum of diameters?
1	UNK	Any	No, exclude assessment
2	Any	UNK	No, exclude assessment
3	CR/PR/SD	PD	No, flag assessment with *
4	PD	PD	Yes
5	CR/PR/SD	CR/PR/SD	Yes

Based on the above considerations, the following algorithm will be used to construct the graph:

1. Select “valid” post-baseline assessments to be included, i.e. for each patient and each assessment repeat the following four steps.
 - 1.1. Check the target lesion response and overall lesion response. If at least one of them is UNK then exclude the whole assessment. Otherwise, go to step 1.2.
 - 1.2. Check the overall lesion response. If it is PD then go to step 1.3. Otherwise go to step 1.4.
 - 1.3. Check target response. If it’s PD then go to step 1.4. Otherwise flag the assessment with * .
 - 1.4. Calculate the % change from baseline in target lesions.
2. For each patient, go through all valid assessments identified in step 1 and find the assessment with best % change from baseline in target lesions. The “best” means best for the patient, i.e. the largest shrinkage or if a patient only has assessments with tumor growth take the assessment where the growth is minimal.
3. Construct the waterfall graph displaying the best % change from baseline for each patient. Patients having only * flagged assessment(s) will be displayed separately.

The graph will be constructed using the data from the investigator/local radiologist assessments.

The best overall response (BOR) will be shown above each of the displayed bars in the graph, if the number of patients displayed in the graph is small enough for the labels to be legible.

The order of the display from left to right will be as follows:

1. Bars under the horizontal axis representing tumor shrinkage
2. Bars above the horizontal axis representing tumor growth
3. “Zero” bars with * symbol.

For each of the 3 categories above, n (%) (where % uses the total number of patients displayed in the graph) will be displayed. If there are any patients with zero change they will be as a separate category following patients with tumor shrinkage.

3 Statistical methods used in reporting

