4.1.4 Efficacy follow-up

Patients who discontinue treatment for reasons other than disease progression or withdrawal of consent for efficacy follow-up, will continue to be followed every 8 weeks \pm 1 week for efficacy (i.e., tumor assessments and PROs) during the first 18 months and every 12 weeks \pm 1 week until 36 months, then change to as clinically indicated until disease progression, death, withdrawal of consent, loss to follow-up, subject/guardian decision. All scans will be acquired and analyzed for primary endpoint locally and will be sent to the Contract Research Organization (CRO) designated by Novartis for central imaging interpretation. If a patient starts a new antineoplastic treatment without withdrawing consent, the patient will continue to be followed for efficacy according to above specified protocol schedule until disease progression, death, withdrawal of consent, loss to follow-up, or subject/guardian decision. For further details please refer to [Table 7-1](#) and [Section 7.1.6](#).

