3.8.1.1 Primary analysis

The primary analysis of PFS will be based on the local radiological assessments (Source 1 in [Table 3-2](#)) up until the cut-off date defined in [Section 2.2](#). The analysis will be performed on the FAS and will use the default censoring and event date options from [Table 3-3](#), with the

exception of the rules for new antineoplastic therapy given, i.e. event/censoring rules will be based on options A(1), B(1), C1(1), C2(1), D(1), E(1), and F(1). In particular, PFS will be censored at the last adequate tumor assessment if a patient didn't have an event or the event occurred after two or more missing tumor assessments (see [Section 2.4.5](#)). In the primary analysis in this study PFS will not be censored if a new antineoplastic therapy is started; instead, an ITT approach will be used and this new antineoplastic therapy will be ignored for the purposes of PFS derivation (and tumor assessments will continue), i.e. option F(1) in [Table 3-3](#) will be used. A sensitivity analysis will be performed censoring PFS at the last adequate tumor assessment prior to start of new antineoplastic therapy, i.e. using option F(2). Discontinuation of study treatment (for any reason) will not be considered as a reason for censoring.

Table 3-3 Options for event dates used in PFS

Situation		Options for end-date (progression or censoring) ¹ (1) = default unless specified differently in the protocol or RAP	Outcome
A	No baseline assessment	(1) Date of randomization/start of treatment ³	Censored
B	Progression at or before next scheduled assessment	(1) Date of progression (2) Date of next scheduled assessment ²	Progressed Progressed
C1	Progression or death after exactly one missing assessment	(1) Date of progression (or death) (2) Date of next scheduled assessment ²	Progressed Progressed
C2	Progression or death after two or more missing assessments	(1) Date of last adequate assessment ² (2) Date of next scheduled assessment ² (3) Date of progression (or death)	Censored Progressed Progressed
D	No progression	(1) Date of last adequate assessment	Censored
E	Treatment discontinuation due to 'Disease progression' without documented progression, i.e. clinical progression based on investigator claim	(1) Ignore clinical progression and follow situations above (2) Date of discontinuation (visit date at which clinical progression was determined)	As per above situations Progressed

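### The waterfall graph in SAP 2.4.7 has no cut-off at new anti-neoplastic therapy, so a bar can show shrinkage produced by the next treatment

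*SAP*

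**What the plan says.** SAP 2.4.7 gives the purpose of the graph: "Waterfall graphs will be used to depict the anti-tumor activity". Only patients with measurable disease at baseline are plotted.

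Step 1 of the algorithm selects the "post-baseline assessments to be included, i.e. for each patient and each assessment repeat the following four steps". The steps apply two filters:

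- Unknown response, target or overall: "If at least one of them is UNK then exclude the whole assessment".
- Overall PD with a target response of CR, PR or SD: the assessment is flagged with an asterisk and no percentage is calculated.

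Step 2 is then to "go through all valid assessments identified in step 1 and find the assessment with best % change from baseline in target lesions". Table 2-2, presented as covering every scenario, sorts assessments by the same two responses. The number and percentage of patients with shrinkage and with growth are shown on the graph. BOR is printed above the bars if there are few enough patients for the labels to be legible.

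On scans after a change of therapy, Protocol 4.1.4 says: "If a patient starts a new antineoplastic treatment without withdrawing consent, the patient will continue to be followed for efficacy". SAP 3.8.1.1 agrees for the primary PFS analysis: "this new antineoplastic therapy will be ignored for the purposes of PFS derivation (and tumor assessments will continue".

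For BOR the SAP does draw a line. SAP 2.4.3 admits "only tumor assessments performed before the start of any further anti-neoplastic therapies". Palliative radiotherapy does not count as such therapy, nor does fulvestrant monotherapy continued as the first new therapy after end of treatment without prior PD. Protocol Appendix 3 (14.3.17) likewise leaves out, as a rule, assessments made after alternative cancer therapy. Both statements concern BOR only.

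**The concern.** Scanning on after a switch suits a PFS analysis that ignores new therapy by design. It does not suit a graph meant to show the activity of the randomized treatment. A maximum-shrinkage rule with no therapy cut-off will pick a scan taken under the next drug whenever that scan shows the largest reduction. The bar would then credit the randomized arm with another drug's effect.

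Two further things follow. A patient whose target lesions only grew on study treatment can move from the growth count to the shrinkage count. And where BOR labels are printed, bar and label can rest on different scans of the same patient.

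The SAP sets a new-therapy cut-off elsewhere when it wants one: ECOG deterioration (3.8.2.8), patient-reported deterioration (3.8.2.9), time to onset of adverse events of special interest (3.9.1.5.1) and a PFS sensitivity analysis (3.8.1.5). SAP 2.4.7 also takes a deliberately conservative line on overall PD with non-PD target lesions. The missing cut-off is out of keeping with both.

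**Working it through.** The plan states no figure to reproduce, so the check is a reading of the rules together and a hand trace.

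**1. Do post-switch scans exist?** Yes. Protocol 4.1.4 and SAP 3.8.1.1 both provide for them. Scheduled scans end at progression, so the exposure lies mainly in patients who start a new therapy before documented PD.

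**2. Does anything in SAP 2.4.7 remove them?** No. The text, Table 2-2 and steps 1.1 to 1.4 depend only on target and overall response. None refers to a date, to the end of study treatment or to subsequent therapy. The scans are not expressly included; they enter because nothing excludes them.

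**3. Does the BOR rule reach the graph?** No. SAP 2.4.3 restricts the assessments used for BOR. SAP 2.4.7 uses BOR as a label, not to choose the scan behind the bar.

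**4. Hand trace on an assumed patient.** Assumptions: measurable disease, no new or worsening non-target lesions, unchanged imaging method, first post-baseline scan more than 7 weeks after randomization, and a new therapy that is neither palliative radiotherapy nor fulvestrant monotherapy.

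| Scan | Sum of diameters | Change from baseline | Target / overall | Table 2-2 | Eligible for BOR |
|---|---|---|---|---|---|
| Baseline | 100 mm | – | – | – | – |
| On study treatment | 95 mm | (95 − 100)/100 = −5% | SD / SD | case 5, calculate | yes |
| After new therapy | 60 mm | (60 − 100)/100 = −40% | PR / PR | case 5, calculate | no |

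- SAP 2.4.7 as written: the larger shrinkage of −5% and −40%, so the bar is −40%.
- With the SAP 2.4.3 cut-off: only −5% remains, so the bar is −5%.
- BOR is SD in both cases, because the second scan is not used for it.

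**5. What cannot be computed.** The documents do not count patients with measurable disease who switch before PD and then have a valid scan with more shrinkage than any earlier one. The size of the effect over the whole graph is therefore unknown.

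**The case against.** **The output is minor.** The waterfall is not a listed endpoint and carries no test. ORR is built on BOR, which already has the cut-off. This stands, and limits the weight of the point.

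**Other documents may settle it.** SAP section 1 places figure shells and programming specifications in separate documents, which were not available; a filter may be there. That is possible. But SAP 2.4.7 sets out the selection rule step by step, and followed as written it gives the wrong bar.

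**An SD label over a deep bar proves nothing.** Correct. SAP 2.4.3 needs two determinations at least 4 weeks apart for PR, so one unconfirmed large reduction on study treatment gives the same picture. Labels are also conditional on legibility. The defect lies in which scans feed the bar.

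**A reader might infer a size.** Protocol 1.2.3.3 gives phase I discontinuation for adverse events as 0% at 300 mg and 13% at 400 mg. Applied to half of 340 patients (170), that is 0 to 0.13 × 170 ≈ 22 bars. The documents do not support this use:

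- This trial starts at 300 mg, and the 0% comes from 9 patients (Table 1-2).
- Stopping alpelisib is not switching therapy; Protocol 6.1.2 lets patients continue fulvestrant.
- Patients without measurable disease are not plotted.
- A bar changes only if a later valid scan shows more shrinkage than all earlier ones.

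**A reader might also infer that the error favours alpelisib**, through more toxicity stops. No figure shows this, and there is an opposite route. Stopping for clinical progression without RECIST evidence is not PD (SAP 2.4.2; Table 3-3, situation E). Such patients stay in follow-up and may start new therapy; if that is commoner on placebo, control would gain.

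**Conclusion.** The point holds as a defect in a stated rule. SAP 2.4.7 as written can plot next-line shrinkage as the activity of study treatment, and can alter the displayed n (%) with shrinkage. Where labels are printed, a bar can rest on scans that its label excludes.

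The effect on one bar can be large (−40% against −5% in the assumed patient). The number of bars affected and the net direction between arms cannot be determined from the documents. The conclusion assumes that no filter has been added in the separate programming documents.

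It would be wrong to read this as a threat to the efficacy conclusions: PFS, OS and ORR do not use the waterfall selection. It is a correction to a descriptive figure.

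**What to change.** Add to step 1 of SAP 2.4.7 that only assessments eligible for BOR under SAP 2.4.3 enter the algorithm. The same two exceptions apply: palliative radiotherapy, and fulvestrant monotherapy continued as the first new therapy after end of treatment without prior PD. No further restriction is needed for this purpose.

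The cost is one sentence and one programming filter. The BOR derivation already needs that filter, and SAP 2.4.3 names the eCRF pages that supply the data. The downside is that a few patients whose only valid scans follow a new therapy may lose their bar. SAP 2.4.7 already excludes patients without valid assessments and explains this in a footnote; the denominator for the percentages would fall accordingly.
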